9.4 Celecoxib (Celebrex) / Placebo (NSC #719627, Alliance IND #107051)

Availability

Celecoxib (NSC 719627) and matching Placebo will be provided free of charge by Pfizer and distributed by the Pharmaceutical Management Branch (PMB), Cancer Therapy Evaluation Program (CTEP), Division of Cancer Treatment and Diagnosis (DCTD), National Cancer Institute (NCI).

Celecoxib and matching Placebo will be supplied in bottles containing 100 – 400mg capsules (Celecoxib) or 100 – 0mg capsules (Placebo) with a child-resistant cap and a tamper-evident seal. Each blinded, patient-specific bottle will be labeled with:

- The protocol number (i.e., “CALGB-80702”)
- The bottle number (i.e., “Bottle 1 of 2”, “Bottle 2 of 2”)
- The number of capsules (i.e., “100 capsules”)
- The patient ID number (e.g., “999999”, where “999999” represents a unique patient identifier assigned at registration)

- The patient initials (i.e., last initial, first initial, middle initial [e.g., "L, FM"])
- The agent identification (i.e., "Celecoxib 400 mg or Placebo")
- A blank line for the pharmacist to enter the patient's name
- Administration instructions (i.e., "Take one capsule once daily with food.")
- Storage instructions (i.e., "Store at room temperature (15°C to 25°C, 59°F to 77°F).")
- Emergency contact instructions
- A Julian date

The Julian date indicates the day the bottle was labeled and shipped and is composed of the last two digits of the calendar year (e.g., 2009 = 09, 2010 = 10) and a day count (e.g., January 1 = 001, December 31 = 365). For example, a bottle labeled and shipped on January 1, 2009 would have a Julian date of '09001' and a bottle labeled and shipped on December 31, 2010 would have a Julian date of '10365'. The Julian date will be used by PMB for recalls. When a lot expires, PMB will determine the last date the expired lot was shipped and will recall all bottles (i.e., both Celecoxib and Placebo) shipped on or before that date thus eliminating any chance of breaking the blind.

The Alliance for Clinical Trials in Oncology holds the IND (#107051) for celecoxib/placebo for this trial. As such, the Alliance follows NCI CTMB policies and guidelines regarding drug distribution, repackaging and shipment of the drug.

Questions about drug orders, transfers, returns, or accountability should be addressed to the PMB by calling [REDACTED] Monday through Friday between 8:30AM and 4:30PM Eastern Time or by emailing [REDACTED] anytime.

Drug Ordering

No blinded starter supplies will be available for this study. Blinded, patient specific clinical supplies will be sent to the registering investigator at the time of randomization and should arrive within approximately 7 to 10 days. This randomization will be performed by the Alliance Statistics and Data Center. The assigned patient study ID number must be recorded by the registering institution for proper bottle dispersion. Once a patient has been registered, the Alliance Statistics and Data Center will electronically transmit a clinical drug request for that patient to the PMB. This request will be entered and transmitted by the Alliance Statistics and Data Center the day the patient is registered and will be processed by the PMB the next business day and shipped the following business day. Shipments within the United States will be sent by FedEx Ground (generally 5 business day delivery) and shipments to Canada will be sent by FedEx (generally one to two day delivery). Thus, if a patient is registered on Monday, the Alliance would enter a clinical drug request for that patient on Monday and PMB would process that request on Tuesday and ship the drug on Wednesday. United States sites could expect to receive their order approximately Tuesday or Wednesday of the following week and Canadian sites could expect to receive their order either Thursday or Friday. Shipments to United States sites can be expedited (i.e., receipt on Thursday in example above) by the provision of an express courier account name and number to the Alliance Statistics and Data Center at the time the patient is randomized.

The initial request will be for **2 – 100 capsule bottles** (a 6 month supply at a dose of one capsule once daily) of Celecoxib or matching Placebo. After five months (one month before needed), sites may reorder an additional **2 – 100 capsule bottles** (a 6 month supply at a dose of one capsule once daily) using the PMB Online Agent Order Processing (OAOP) application [REDACTED]. Access to OAOP requires the establishment of a CTEP Identity and Access Management (IAM) account [REDACTED] and the maintenance of an "active" account status and a "current"

password. The protocol number (i.e., CALGB-80702), the assigned patient ID number (e.g., "999999"), the patient initials (e.g., "L, FM"), and the number of bottles remaining from the previous shipment should be entered on each order. **Please note that a maximum of six shipments (12 bottles of 100 capsules), a sufficient quantity to complete three years of therapy, will be provided for each patient.**

All drug orders will be shipped directly to the registering physician at the shipping address listed on their most recent Supplemental Investigator Data Form (IDF) on file with CTEP. The registering investigator must maintain an active investigator status with CTEP, DCTD through the annual submission of an FDA Form 1572 (Statement of Investigator), a Curriculum Vitae, a Supplemental Investigator Data Form (IDF), and a Financial Disclosure Form (FDF)

CALGB-80702 Shipment Schedule

Patient Randomized with Alliance	Initial e-Order Transmitted by Alliance	Initial e-Order Received and Approved by PMB	Initial Order Shipped by PMB	Initial Order Received at Site**
Monday	Monday	Tuesday	Wednesday	Tuesday
Tuesday	Tuesday	Wednesday	Thursday	Wednesday
Wednesday	Wednesday	Thursday	Friday	Thursday
Thursday	Thursday	Friday	Monday	Friday
Friday	Friday	Monday	Tuesday	Monday

**** Arrival time approximate / shipments sent by FedEx Ground**

How Supplied

"Celecoxib" and matching "Placebo" are supplied as a size 0 white to off-white opaque hard gelatin capsule for oral administration. Each tamper-evident, child-resistant, 180ml, square, white, opaque, high-density polyethylene (HDPE) bottle contains 100 capsules. For "Celecoxib", each capsule contains 400mg of celecoxib with croscarmellose sodium, edible inks, gelatin, lactose monohydrate, magnesium stearate, povidone, and sodium lauryl sulfate. For "Placebo", each capsule contains croscarmellose sodium, edible inks, gelatin, lactose monohydrate, magnesium stearate, povidone, and sodium lauryl sulfate.

Storage and Stability

"Celecoxib" and matching "Placebo" are shipped at room temperature by US Priority Mail. The capsules should be stored at controlled room temperature (15°C to 25°C, 59°F to 77°F). The intact bottles of 100 capsules are stable for five years from date of manufacture when stored at controlled room temperature.

Route of Administration

Oral. Celecoxib/placebo at doses of 400mg orally once daily should be administered with food to improve absorption.

Drug Transfers

Bottles may NOT be transferred from one patient to another patient or from one protocol to another protocol. All other transfers (e.g., a patient moves from one participating clinical site to another participating clinical site, the registering investigator for a patient changes) must be approved in advance by the PMB. To obtain an approval for transfer, investigators should complete and submit to the PMB (fax number [REDACTED]) a Transfer Investigational Agent Form available on the CTEP home page [REDACTED]. The patient ID number (e.g., "999999") and the patient initials (e.g., "L,FM") must be entered in the "Received on NCI Protocol No." and the "Transferred to NCI Protocol No." fields in addition to the protocol

number (i.e., "CALGB-80702"). The Julian date / order number (e.g., 10365-9999) should be entered in the "Lot Number" field.

Drug Returns

Only undispensed clinical supplies should be returned to the PMB. When it is necessary to return study drug (e.g., sealed bottles remaining when a patient permanently discontinues protocol treatment, expired bottles recalled by the PMB), investigators should return the study drug to the PMB using the NCI Return Drug List available on the CTEP home page [REDACTED]. The patient ID number (e.g., "999999"), the patient initials (e.g., "L, FM"), and the Julian date / order number (e.g., 10365-9999) should be entered in the "Lot Number" field. A separate line item is required for each patient ID number (e.g., "999999") being returned. **Dispensed bottles with remaining tablets should be documented in the patient-specific NCI Investigational Agent Accountability Record (i.e., logged is as "returned by patient" and logged out as "destroyed on site") and destroyed on site in accordance with institutional policy.**

Drug Accountability

The investigator, or a responsible party designated by the investigator, must maintain a careful record of the receipt, disposition, and return of all drugs received from the PMB using the NCI Investigational Agent Accountability Record available on the CTEP home page [REDACTED]. A separate **Oral** NCI Investigational Agent Accountability Record must be maintained for each patient ID number (e.g., "999999") on this protocol. The combination Julian date / order number in the upper right hand corner of the patient-specific bottle label (e.g., 10365-9999) should be recorded as the lot number.

Unblinding Procedures

Unblinding can be done only in the case of an emergency. Follow the directions below to unblind patient treatment. Please note that, if treatment is unblinded due to an emergency, the patient must permanently discontinue all protocol therapy.

Emergency Unblinding Procedures

Examples of emergencies include ...

1) a life threatening unexpected adverse event that is at least possibly related to the investigational agent and for which unblinding would influence treatment decisions

OR

2) a medication error, such as an accidental overdose.

Expected adverse events are listed in the "Toxicities" section below.

Contact the Alliance Executive Office on call by calling [contact], pressing 1 to speak with an operator, and then asking for [name] to return the call.

The institution must provide the following information to the Alliance Executive Officer:

- CALGB study ID (i.e., "CALGB-80702")
- Patient study ID number (e.g., "999999")
- Patient initials (e.g., "L,FM")
- Institution name
- Name and telephone number of treating physician
- Name and contact information of person requesting the unblinding procedure
- Name and contact information of person to inform of treatment assignment
- Reason for emergency unblinding

Please remember that emergency unblinding request may be authorized only by an Alliance Executive Officer, and emergency unblinding applies only if unblinding would influence management of the medical situation.

After authorization by a designated Alliance Approving Physician, the treatment assignment will be provided to the contact person.

Toxicities

Celecoxib/placebo is generally well tolerated. The most common toxicity reported in arthritis trials is a headache. Other possible toxicities include peripheral edema, insomnia, dizziness, skin rash, dyspepsia, diarrhea, abdominal pain, nausea, flatulence, back pain, upper respiratory tract infection, sinusitis, pharyngitis, and rhinitis.

The incidence of GI ulcers documented by endoscopy in arthritis trials is 7%. GI bleeding is more likely to occur in patients with a history of peptic ulcer disease and/or GI bleeding. The risk of GI ulceration, bleeding or perforation with celecoxib is increased with concomitant use of aspirin. Chronic use of aspirin (>100 mg/day) or other NSAIDs is not allowed on this trial (see [Section 4.2](#)).

As is the case with non-selective NSAIDs, celecoxib may be associated with nephrotoxicity in patients in whom renal prostaglandins are important in maintenance of renal blood flow. Specifically, patients with pre-existing renal dysfunction, heart failure, liver dysfunction or dehydration, elderly patients, or patients taking diuretics or ACE inhibitors are at the greatest risk for significant inhibition of renal blood flow and nephrotoxicity. In addition, long-term use of NSAIDs has been associated with renal injury, including renal papillary necrosis. Unlike other non-selective NSAIDs, celecoxib does not appear to inhibit platelet aggregation.

A safety analysis performed in December, 2004, of several long-term celecoxib trials was conducted following the removal of rofecoxib from the market because of an increased risk of adverse cardiovascular events. The celecoxib analysis resulted in the suspension of drug use for patients enrolled in the Adenoma Prevention with Celecoxib (APC) trial. In this trial, the risk of cardiovascular death, myocardial infarction or stroke in the celecoxib groups was 2-3 times higher than the risk in the placebo group. This increased hazard with celecoxib was not observed in another long-term trial.

Drug Interactions

Celecoxib is metabolized in the liver by cytochrome P450 2C9. Drugs that inhibit (e.g., fluconazole) or induce (e.g., rifampin) the 2C9 isoenzyme might be expected to result in increased toxicity or decreased effect of celecoxib, respectively. In addition, celecoxib is reported to inhibit the 2D6 isoenzyme, potentially enhancing the effects of drugs metabolized by this isoenzyme.

The following describes possible drug interactions:

ACE-inhibitors: NSAIDs may diminish the antihypertensive effect of ACE-inhibitors.

Coumadin: Celecoxib does not alter PT/INR; there have been reports of prolonged prothrombin time and bleeding in elderly patients taking both coumadin and celecoxib.

Fluconazole: Concomitant administration of celecoxib and fluconazole results in a two-fold increase in celecoxib levels.

Lithium: Concomitant administration of celecoxib and lithium results in an increase in steady-state lithium levels.

10.0 ANCILLARY THERAPY

10.1 Supportive Care

Patients should receive *full supportive care*, including transfusions of blood and blood products, antibiotics, antiemetics, etc., when appropriate. The use of epoetin products is not allowed. The reason(s) for treatment, dosage, and the dates of treatment should be recorded on Form C-1954 via Medidata Rave®.

10.2 Hormonal/other chemotherapeutic agents

Treatment with *hormones or other chemotherapeutic agents* for cancer treatment may not be administered. Exceptions allowing usage of hormones and other chemotherapeutic agents include, but not limited to, steroid given for adrenal failure, hypersensitivity reactions or other non-cancer related conditions; hormones administered for non-disease-related conditions (e.g., but not limited to, insulin for diabetes); intermittent use of dexamethasone as an antiemetic; or methotrexate or other DMARDs (disease-modifying anti-rheumatic drugs) used for rheumatological conditions.”

10.3 Loperamide

For symptoms of diarrhea and/or abdominal cramping that occur at any time during a treatment cycle, patients will be instructed to begin taking loperamide. Loperamide should be started at the earliest sign of (1) a poorly formed or loose stool or (2) the occurrence of 1 to 2 more bowel movements than usual in 1 day or (3) an increase in stool volume or liquidity. Loperamide should be taken in the following manner: 4 mg at the first onset of diarrhea, then 2 mg every 2 hours around the clock until diarrhea-free for at least 12 hours. Patients may take loperamide 4 mg every 4 hours during the night. The maximum daily dose of loperamide is 16 mg/day. Patients should be advised to obtain loperamide at the initial treatment visit so that they have sufficient supply on hand in case antidiarrheal support is required. Additional antidiarrheal measures may be used at the discretion of the treating physician. Patients should be instructed to increase fluid intake to help maintain fluid and electrolyte balance during episodes of diarrhea.

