1.4 FOLFOX for colon cancer

Oxaliplatin administration has been coupled with 5-fluorouracil infusion mainly in two ways. In the method developed by de Gramont, patients are given a loading dose of 400 mg/m² 5-fluorouracil as a bolus injection administered after a two-hour leucovorin infusion at a dose of 400 mg/m². The loading dose is then followed by a 22-hour 5-fluorouracil infusion of 600 mg/m² via a pump programmed to provide a constant drug infusion rate.⁹ This program is repeated on two consecutive days every two weeks. A version termed FOLFOX-4 utilizes 85 mg/m² of oxaliplatin. In order to ease the administration and reduce the number of clinic visits, a modified version, FOLFOX-6, has been routinely used in clinical practice and recent clinical trials. Patients receive a loading dose of 400 mg/m² 5-fluorouracil as a bolus injection given after a two-hour leucovorin infusion at a dose of 400 mg/m². The loading dose is then followed by a

46-hour 5-fluorouracil infusion of 2,400 mg/m² via a pump programmed to provide a constant drug infusion rate.¹⁰⁻¹²

Randomized clinical trials have consistently shown FOLFOX to result in superior response rates and times to disease progression compared to fluorouracil and leucovorin alone when given as first^{9,13,14} or second-line¹⁵ treatment of advanced colorectal cancer. The NCCTG trial N9741 treated 265 patients with advanced colorectal cancer not previously treated with chemotherapy for advanced disease using the FOLFOX-4 regimen. In this trial, IFL was used as the comparator arm.¹⁶ The FOLFOX regimen resulted in a statistically significant advantage in time to progression from a median of 6.9 to 8.8 months ($p = .0009$), a response rate advantage of 29% versus 38% ($p = .03$), and a median survival advantage of 14.1 versus 18.6 months ($p = .002$) over IFL. Toxicity also favored FOLFOX over IFL with significantly less grade 3 or greater nausea (6 versus 15%), vomiting (4 versus 12%), diarrhea (13 versus 33%) and 1.8 % versus 4.5% 60-day all-cause mortality observed. More paresthesias were observed with FOLFOX than with IFL (18% versus 2%).

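### Followed for a full day, the Section 10.3 loperamide schedule totals 24 to 26 mg against the 16 mg/day maximum in the same paragraph, and the text does not say which governs.

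*Combined protocol and SAP*

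**What the plan says.** Section 10.3 (Loperamide) puts all of the following in one paragraph.

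- Trigger: "Loperamide should be started at the earliest sign of (1) a poorly formed or loose stool". One or two extra bowel movements in a day, or an increase in stool volume or liquidity, also count.
- First dose: "4 mg at the first onset of diarrhea".
- Continuation and stop rule: "then 2 mg every 2 hours around the clock until diarrhea-free for at least 12 hours".
- Night option: "Patients may take loperamide 4 mg every 4 hours during the night".
- Ceiling: "The maximum daily dose of loperamide is 16 mg/day".

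The paragraph does not rank the schedule against the ceiling. It does not say whether a day is a calendar day or the 24 hours from the first dose. No other section of the protocol or its appendices settles either question.

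**The concern.** The schedule and the ceiling are both explicit figures, and over a full day they disagree. A patient who keeps to the schedule goes over the ceiling. A patient who stops at the ceiling while diarrhea continues keeps neither the dosing interval nor the stop rule.

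The paragraph describes what patients will be told and advises them to have a supply to hand, so the question may well arise away from the clinic. Sites could also resolve it differently. Section 8.3.1 makes FOLFOX delay and dose reduction depend on diarrhea grade, so uneven antidiarrheal use could plausibly affect recorded toxicity and delivered FOLFOX dose. The documents contain nothing from which to size that effect.

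**Working it through.** **Inputs, all from Section 10.3.** First dose 4 mg at hour 0. Then 2 mg at hours 2, 4, 6 and so on, which is 1 mg per hour. Night option 4 mg per 4 hours, also 1 mg per hour, taken here as replacing the two-hourly doses. Dosing stops once 12 hours have passed since the last loose stool. Ceiling 16 mg/day.

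**Does the schedule reproduce the 16 mg figure?** The cumulative dose at even hour h is 4 + 2 × (h/2) = 4 + h mg.

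- Hour 12: 4 + 12 = 16 mg, equal to the ceiling.
- Hour 14: 4 + 14 = 18 mg, the first total above it.
- First 24 hours (doses at hours 0 to 22): 4 + 11 × 2 = 26 mg. The excess is 10 mg, and 10/16 = 63%. Counting the hour-24 dose as well gives 28 mg.
- Each later full day: 12 × 2 = 24 mg. The excess is 8 mg, and 8/16 = 50%.
- Night option: because the hourly rate is the same, nights of 6, 8, 10 or 12 hours all leave the totals at 26 mg and 24 mg.

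The 16 mg figure is therefore met only if dosing ends at about hour 12.

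**How long must an episode last for the conflict to arise?** Let L be the time of the last loose stool, in hours after the first dose. Doses are taken before hour L + 12. The last column adds any dose that falls exactly at that hour.

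| L (hours) | Course total (mg) | Total if a dose exactly at L + 12 is counted (mg) |
|---|---|---|
| 0 | 14 | 16 |
| 1 | 16 | 16 |
| 2 | 16 | 18 |
| 3 | 18 | 18 |
| 6 | 20 | 22 |
| 12 | 26 | 28 |

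With the day counted from the first dose, both instructions can be met up to L of about 2 hours and not beyond. At exactly 2 hours the answer depends on whether the hour-14 dose is taken.

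**Calendar-day reading.** Assume onset on each clock hour from 0 to 23, all equally likely, and do not count a dose exactly at L + 12. The number of onset hours, out of 24, for which some calendar day exceeds 16 mg is:

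- L = 0 or 2: 0 of 24
- L = 4 or 6: 10 of 24
- L = 12: 16 of 24
- L = 24: 24 of 24

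So the definition of a day changes who is affected, but neither definition removes the conflict.

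**Share of patients.** This needs the distribution of L, which the documents do not give. If every episode had L of 2 hours or less, the share would be 0% (no dose taken exactly at L + 12). If every episode had L of 24 hours, it would be 100% under either definition of a day.

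**The case against.** The best defense is that a maximum stated after a schedule is naturally read as a limit on it: the patient follows the schedule until 16 mg is reached and then stops for that day. Short episodes never meet the limit, so it is not true that the two instructions can never both be followed. Both points stand, and they narrow the criticism. They do not remove it. The text does not say that the ceiling overrides. If it does, a patient whose diarrhea continues takes the last permitted dose at hour 12 and then nothing until the day turns over. That breaks the two-hourly interval and the stop rule, and the moment the day turns over is itself undefined.

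A second objection concerns reach. The paragraph applies to every arm and celecoxib/placebo is double-blind (Section 7.0), so no route to bias in the disease-free survival comparison is apparent. That stands, and no such bias is claimed. The instruction sheet that patients actually receive is also not in the documents available, so it is not shown that patients were left to resolve the conflict themselves.

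A third objection is timing. Section 13.1 speaks of enrollment in the past tense and lists interim analyses up to 09/2018, and Appendix VI, Section 2.0, gives this trial's accrual period as 6/2010 to 6/2015. FOLFOX runs for 6 or 12 cycles of 14 days (Section 7.0), so few or no patients are likely to be receiving it still. This lowers the urgency but does not make the paragraph consistent.

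**Conclusion.** The point holds as an internal contradiction. Over a full day the schedule gives 26 mg (first day) or 24 mg (later days) against 16 mg, and the maximum is passed at the hour-14 dose. On a day counted from the first dose, the conflict arises when loose stools continue more than about 2 hours after that dose. Shorter episodes, at 14 to 16 mg, comply with both instructions. The result rests only on the figures in Section 10.3 and on reading the night option as a replacement for the two-hourly doses.

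A reader might infer that most patients given loperamide would exceed the maximum. The documents do not support that. The low trigger brings in brief, mild episodes as well as longer ones, and no duration is given for either. A reader might also take the 13% rate of grade 3 or greater diarrhea in Section 1.4 and count 0.13 × 2,500 = 325 patients. That rate is an incidence from FOLFOX-4 in advanced disease. It is neither an episode duration nor a rate for this adjuvant population, so 325 does not count patients above 16 mg.

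Severity: a low-urgency wording correction, since accrual appears complete. No view is taken on which dose or limit is right.

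**What to change.** Reconcile the schedule, night option, stop rule and daily maximum in Section 10.3 so that they can be followed together. State which instruction governs when they meet, and define a day as either a calendar day or 24 hours from the first dose. Carry the same wording into any patient instruction still in use. The study chairs and pharmacy decide the clinical content.

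The cost is a one-paragraph amendment and matching patient wording, with no added procedures, data or patients. If nobody is still receiving FOLFOX, the correction serves mainly to keep the protocol text consistent.
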